15. SAFETY OUTCOMES

All tables for safety outcomes will be based on the SAF.

All listings will be based on the RND analysis set.

There will be no statistical comparisons between the treatment groups for safety data.

15.1. ADVERSE EVENTS

Adverse Events (AEs) will be coded using Medical Dictionary for Regulatory Activities (MedDRA) central coding dictionary, Version 21.0.

Treatment emergent adverse events (TEAEs) are defined as AEs that started on or after the first dose of study medication and prior to the last date of study medication + 125 days (inclusive).

See 17 for handling of partial dates for AEs. In the case where it is not possible to define an AE as treatment emergent or not, the AE will be classified by the worst case; i.e. treatment emergent. An overall summary of number of subjects within each of the categories described in the subsection below, will be provided as specified in the templates. Listings will include TEAEs and Non-TEAEs.

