The study will consist of a maximum 4-week Screening Period, followed by a 12-week double-blind treatment evaluation period, followed by a 16-week safety follow-up period, for a maximum study duration of approximately 32 weeks or 224 days per subject. Eligible subjects will be randomised on Day 1 of Week 0 and receive study treatment administered sc on Day 1 of Week 0, Week 2 (loading dose), Week 6 and Week 10. Subjects will return on Week 12 for an End of Treatment (EoT) visit during which efficacy and safety assessments will be performed. Subjects will have a follow-up visit 16 weeks after the EoT visit.

Number of Investigators and Study Centres:

Up to 10 Investigators and 10 study centres are expected to participate in this study.

Number of Subjects:

Approximately 70 subjects will be screened to achieve 42 subjects randomly assigned to study treatment (36 on active treatment and 6 on placebo) and 42 evaluable subjects for an estimated total of 36 evaluable subjects on the active treatment arm and 6 evaluable subjects in the placebo treatment arm.

Treatment Groups and Duration:

Test product, dose and mode of administration:

Namilumab 150 mg sc administered at Weeks 0, 2, 6 and 10.

Reference therapy, dose and mode of administration:

Matching placebo solution sc administered at Weeks 0, 2, 6 and 10.

Statistical Methods:

The primary endpoint will be ASAS20. Based on literature data, the prior for the placebo and namilumab groups will follow a beta distribution with mean of 0.3 and 0.6, respectively. Weighting for the priors will be equivalent to 20 and 5 subjects, respectively. Sample size is the smallest sample size so that P{ θ act > θ pbo| Y(HA)} >0.927 with probability 0.9, assuming true response rates of 0.3 and 0.6 for the control and namilumab arms, respectively. For a 6:1 randomisation, 42 patients need to be randomised.

Efficacy endpoints will be summarised by treatment group and visit. The posterior distribution of the primary endpoint will be computed using the conjugate priors, and the mean, standard deviation, and 5th, 10th, 25th, 50th, 75th, 90th, and 95th percentiles of the posterior distribution will be presented.

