8.3.1 Time Period and Frequency for Collecting AE and SAE Information

All SAEs will be collected from the signing of the ICF until the follow-up visit at the time points specified in the SoA (Section 1.3).

All AEs will be collected from the signing of the ICF until the follow-up visit at the time points specified in the SoA (Section 1.3).

All SAEs will be recorded and reported to the Sponsor or designee within 24 hours, as indicated in Appendix 4. The Investigator will submit any updated SAE data to the Sponsor within 24 hours of it being available.

Investigators are not obligated to actively seek AE or SAE after conclusion of the study participation. However, if the Investigator learns of any SAE, including a death, at any time after a subject has been discharged from the study, and he/she considers the event to be reasonably

related to the study treatment or study participation, the Investigator must promptly notify the Sponsor.

The method of recording, evaluating and assessing causality of AE and SAE and the procedures for completing and transmitting SAE reports are provided in Appendix 4.

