9.4.2 Safety Analyses

All safety analyses will be performed on the Safety Analysis Set.

TEAEs are defined as AEs that first occurred or worsened in severity after the first administration of study treatment and prior to 125 days after the last administration of study treatment.

AEs will be coded using the Medical Dictionary for Regulatory Activities (MedDRA). For each study treatment, numbers of TEAEs and incidence rates will be tabulated by preferred term and system organ class.

TEAEs by maximum severity, TEAEs by relationship to study treatment, SAEs, TEAEs leading to death and TEAEs leading to discontinuation of study treatment will be tabulated for each treatment group. Commonly occurring TEAEs, i.e., those that occur in 5% or more of the subjects in either treatment group, will be summarised using descriptive statistics.

All laboratory test results, vital signs measurements, ECG results, weight and body mass index (BMI) will be summarised for each treatment group using descriptive statistics at each scheduled visit for raw numbers and change from baseline. The incidence of treatment-emergent abnormal laboratory, vital sign and ECG values will also be summarised using descriptive statistics.

visit for raw numbers and change from baseline. The incidence of treatment-emergent abnormal laboratory, vital sign and ECG values will also be summarised using descriptive statistics.

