- The causality assessment is one of the criteria used when determining regulatory reporting requirements.

Follow-up of AEs and SAEs

- The Investigator is obligated to perform or arrange for the conduct of supplemental measurements and/or evaluations as medically indicated or as requested by the CRO to elucidate the nature and/or causality of the AE or SAE as fully as possible. This may include additional laboratory tests or investigations, histopathological examinations, or consultation with other health care professionals.
- If a subject dies during participation in the study or during a recognised follow-up period, the Investigator will provide the CRO with a copy of any postmortem findings including histopathology.
- New or updated information will be recorded in the originally completed CRF.
- The Investigator will submit any updated SAE data to the Sponsor within 24 hours of receipt of the information.

Reporting of SAEs

SAE Reporting to the Medical Monitor via an Electronic Data Collection Tool

- The primary mechanism for reporting an SAE to the Medical Monitor will be the electronic data collection tool.
- If the electronic system is unavailable for more than 24 hours, then the study centre will use the paper SAE data collection tool (see next section).
- The study centre will enter the SAE data into the electronic system as soon as it becomes available.
- After the study is completed at a given study centre, the electronic data collection tool will be taken off-line to prevent the entry of new data or changes to existing data.
- If a study centre receives a report of a new SAE from a subject or receives updated data on a previously reported SAE after the electronic data collection tool has been taken off-line, then the study centre can report this information on a paper SAE form (see next section) or to the CRO Safety Team by telephone/fax or email.
- Contacts for SAE reporting can be found in the safety paper forms for the sites.

SAE Reporting to the Medical Monitor via Paper CRF

- The secondary (backup) mechanism for reporting an SAE to the Medical Monitor will be via a paper CRF.
- Facsimile transmission of the SAE paper CRF is the preferred method to transmit this information to the Medical Monitor.
- In rare circumstances and in the absence of facsimile equipment, notification by telephone is acceptable with a copy of the SAE data collection tool sent by overnight mail or courier service.

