1. INTRODUCTION

This document describes the rules and conventions to be used in the presentation and analysis of efficacy and safety data for Protocol IZN-101. It describes the data to be summarized and analysed, including specifics of the statistical analyses to be performed.

This statistical analysis plan (SAP) is based on protocol version 3 (Amendment 2), dated 05Jul2018.

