3.3. CHANGES TO ANALYSIS FROM PROTOCOL

Full analysis set modified

- The full analysis set (FAS) was defined in the protocol as "All subjects randomly assigned to study treatment and who take at least 1 dose of study treatment and have specific post-baseline assessments available". This has been updated in Section 5.3 of this SAP to be "The full analysis set (FAS) will contain all subjects in the all randomised set (RND) who received at least one dose of study medication".
- The reason for this change is that all subjects with missing data at week 12 for efficacy will be considered as non-responders (as per protocol definition) thus they will all be included in the FAS if randomised and treated.
- Date of agreement of change is 12April2019

Document:	x:\biostatistics\documentation\sap\pya18238_izana_izn-10	1_sap_v1_0_2019050.docx	
Author:		Version Number:	1.0
		Version Date:	07May2019
Template No.: CS_TP_BS016 Revision 5		Reference: CS_W	I_BS00

Effective Date: 01Apr2018

Per-protocol analysis set modified

- The per protocol analysis set was defined in the protocol as "All subjects in the Full Analysis Set that have week 10 efficacy data." This has been updated in Section 5.3 of this SAP to be "The per-protocol analysis set (PPAS) will contain all subjects in the COM who did not experience any protocol deviations that might affect the efficacy results."
- The reasons for this change are that there was a typographical error in the definition (week 10 instead of week 12) and that the goal of the per-protocol analysis is also to investigate the effect of the compound under investigation in patients who did not violate the protocol.
- Date of agreement of change 12April2019

Interim analysis for strategic purposes

- An interim analysis for strategic purposes is added to obtain preliminary results once all randomized subjects have completed the week 12 assessments.
- Date of agreement of change 12April2019

Primary endpoint definition amendment

- The definition has been amended to: "A subject with an improvement from baseline of at least 20% and an absolute improvement of at least 10 units on a 0-100 VAS in at least 3 of the following four domains collected on the eCRF and no worsening in the fourth domain."
- The amendment is due to an improper definition in the protocol.
- Date of agreement of change 12April2019

ASAS70 analysis removed

- ASAS70 endpoint has been removed as it is not a validated measure
- Date of agreement of change 12April2019

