16. DATA NOT SUMMARIZED OR PRESENTED

The other variables and/or domains not summarized or presented are:

• Comments

These domains and/or variables will not be summarized or presented but will be available in the clinical study database.

Document: x:\biostatistics\documentation\sap\pya18238_izana_izn-101_sap_v1_0_2019050.docx

Author:

Version Number: 1.0 Version Date: 07May2019 Reference: CS_WI_BS00

Template No.: CS_TP_BS016 Revision 5

Effective Date: 01Apr2018

17. **PARTIAL DATE CONVENTIONS**

Imputed dates will NOT be presented in the listings.

ALGORITHM FOR TREATMENT EMERGENCE OF ADVERSE EVENTS:

START DATE	STOP DATE	ACTION
Known	Known	If start date < study med start date, then not TEAE If start date >= study med start date up to 125 after study med stop date, then TEAE
	Partial	If start date < study med start date, then not TEAE If start date >= study med start date up to 125 after study med stop date, then TEAE
	Missing	If start date < study med start date, then not TEAE If start date >= study med start date up to 125 after study med stop date, then TEAE
Partial, but known components show that it cannot be on or after study med start date	Known	Not TEAE
	Partial	Not TEAE
	Missing	Not TEAE
Partial, could be on or after study med start date	Known	If stop date < study med start date, then not TEAE If stop date >= study med start date up to 125 after study med stop date, then TEAE
	Partial	Impute stop date as latest possible date (i.e. last day

Document: x:\biostatistics\documentation\sap\pya18238_izana_izn-101_sap_v1_0_2019050.docx

Author:

Version Number: Version Date: 07May2019 Reference: CS_WI_BS00

1.0

Template No.: CS_TP_BS016 Revision 5

Effective Date: 01Apr2018

Page 34 of 36

	-	
START DATE	STOP	ACTION
	DATE	
		of month if day unknown or 31st December if day
		and month are unknown), then:
		If stop date < study med start date, then not TEAE
		If stop date >= study med start date, then TEAE
	Missing	Assumed TEAE
Missing	Known	If stop date < study med start date, then not TEAE
Missing	Known	If stop date < study med start date, then not TEAE If stop date >= study med start date, then TEAE
Missing	Known Partial	If stop date < study med start date, then not TEAE If stop date >= study med start date, then TEAE Impute stop date as latest possible date (i.e. last day

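### The SAP omits the protocol's worsening limb from its treatment-emergent definition without declaring it, so pre-dose adverse events that worsen after dosing may be left out of the TEAE summaries

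*SAP*

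**What the plan says.** Protocol Section 9.4.2 gives a definition with two limbs, onset and worsening: "TEAEs are defined as AEs that first occurred or worsened in severity after the first administration of study treatment". The window closes 125 days after the last administration.

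SAP Section 15.1 has one limb: "Treatment emergent adverse events (TEAEs) are defined as AEs that started on or after the first dose of study medication". It keeps the 125-day window. The treatment-emergence algorithm in SAP Section 17 applies the same rule: "If start date < study med start date, then not TEAE". That line is repeated for a known, a partial and a missing stop date.

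The SAP says that it "is based on protocol version 3 (Amendment 2), dated 05Jul2018", which is the protocol version containing the worsening limb. SAP Section 3.3 lists five changes from the protocol: the full analysis set, the per-protocol set, the added interim analysis, the ASAS20 definition and the removal of ASAS70. The TEAE definition is not among them.

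On collection, Protocol Section 8.3.1 says: "All AEs will be collected from the signing of the ICF until the follow-up visit". On updating an event already reported, Protocol Appendix 4 says: "New or updated information will be recorded in the originally completed CRF".

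**The concern.** Adverse events are recorded before dosing as well as after it, so some may be open on Day 1. If one of these becomes more severe after the first injection, the protocol makes it treatment-emergent and the SAP rule does not. Programmers will follow the SAP.

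Safety and tolerability is a secondary objective. The SAP's adverse event summaries are built on TEAEs: incidence by system organ class and preferred term, maximum severity, relationship to study medication, serious TEAEs and events of special interest. An event that misses the TEAE flag misses all of these. The safety definition is narrower than the one in the approved protocol, and the document that should record the change is silent about it.

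**Working it through.** The plan states no figure on this point, so there is none to reproduce. The check is a comparison of the two rules.

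**1. Same event, two rules.** All cases fall inside the 125-day window and have a known start date.

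| Event | Protocol 9.4.2 | SAP 15.1 and 17 |
|---|---|---|
| Starts after first dose | TEAE | TEAE |
| Starts before first dose, severity does not increase | Not TEAE | Not TEAE |
| Starts before first dose, worsens after it, worsening entered as a new record with a post-dose start date | TEAE | TEAE |
| Starts before first dose, worsens after it, worsening kept on the original record | TEAE | Not TEAE |

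The rules part only in the last row, and there the SAP count can only equal or fall below the protocol count.

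**2. Does anything else in the SAP restore the last row?**
- The worst-case rule in 15.1 applies only when treatment emergence cannot be determined. A known pre-dose start date determines it.
- The severity and relationship rules in 15.1.1.1 and 15.1.1.2 grade events within the TEAE summaries. They do not reclassify an event.
- Severity is not an input to any row of the Section 17 algorithm.

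**3. Can such events arise?** Collection starts at consent. The Protocol Synopsis says: "The study will consist of a maximum 4-week Screening Period". The notes to the Schedule of Activities add that screening may last only 1 week for subjects who already meet all criteria. The pre-dose window is therefore roughly 1 to 4 weeks. The documents show that such events can occur. They do not show that they will.

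**4. Size per subject.** Planned arms are 36 on namilumab and 6 on placebo.
- One namilumab subject: 1/36 = 2.8%.
- One placebo subject: 1/6 = 16.7%.
- Protocol 9.4.2 also plans a summary of TEAEs seen in at least 5% of either arm. On namilumab that takes 2 of 36 (5.6%). If one of those two is lost, the term stands at 2.8% and leaves that summary unless a placebo subject also has it.

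**5. Illustrative range, on assumed rates only.** Suppose 10% to 30% of subjects have an event starting in screening, 10% to 30% of those worsen after dosing, and every worsening stays on the original record. The expected number of subjects affected is then:
- namilumab: 36 × 0.10 × 0.10 = 0.4 to 36 × 0.30 × 0.30 = 3.2;
- placebo: 6 × 0.10 × 0.10 = 0.06 to 6 × 0.30 × 0.30 = 0.5.

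None of these rates comes from the documents. If sites open new records for worsening, the numbers fall towards zero.

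**The case against.** The strongest reply concerns recording. Protocol Appendix 4 asks for a separate entry for each event and assigns each one a single intensity category. It treats exacerbation of a pre-existing condition as an adverse event, and it excludes day-to-day fluctuation only where there is no worsening. Read together, these clauses suggest that a worsening becomes its own record with a post-dose start date, which the SAP rule would count. SAP 15.1.1.1 can already handle several records under one term. This stands as far as it goes, and it covers exacerbated medical-history conditions well. But the same appendix sends updates to the original form and never says that an increase in severity of an open event needs a new start date. The recording rule is ambiguous, and eCRF completion instructions are not in the documents.

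The second reply concerns scope, and most of it stands. Non-TEAEs appear in the listings. Events leading to discontinuation or death have their own listings, not tables, although the overall summary in 15.1 counts subjects in each category. Laboratory, ECG, breathlessness, spirometry and oxygen saturation changes from baseline are summarised without any TEAE flag, so neutrophil falls and respiratory decline are partly covered by other routes. There is no between-arm testing of safety data, and the rule is the same in both arms.

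Third, the SAP is slightly wider than the protocol elsewhere. It counts onset on the day of first dose, includes day 125, counts a recurrence that starts after dosing, and treats indeterminable cases as emergent. That is correct, but none of it brings back an event with a known pre-dose start date.

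**Conclusion.** The SAP definition contradicts the protocol definition, the contradiction is carried into the programming algorithm, and it is not declared. That much is certain from the text.

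The consequence is conditional. An event starting between consent and first dose and worsening after dosing may be absent from the TEAE summaries if the worsening is kept on the original record. For this class of event the direction is fixed and the size is unknown.

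A reader might infer that treatment-emergent toxicity is undercounted in this trial, or that every adverse event output is affected. The documents support neither. The first needs such events to occur and to be recorded in one particular way, and neither is established. The second overlooks the listings and the summaries that do not use the TEAE flag. Nor can one say that total TEAE counts are biased downwards, because the SAP's other differences push the opposite way by an unknown amount.

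The change should be made because the contradiction is plain and the remedy is small, not because a loss has been shown.

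**What to change.** 1. In SAP 15.1, define a TEAE as an event that started, or worsened in severity, on or after the first dose, within the existing 125-day window.
2. In SAP Section 17, add a branch: start date before first dose, with a severity increase on or after first dose and within the window, gives a TEAE dated at the worsening.
3. State how a worsening is recorded. Either the post-dose severity increase is entered as a separate adverse event record with its own start date, or the date of the increase is captured on the existing record. Without one of these, the new branch has no date to work on.
4. Query the events already in the database that were open at first dose, so that the rule applies to them too.

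If the sponsor does intend a start-date-only rule, it should be listed and justified in SAP 3.3. That would cure the silence but leave the SAP narrower than the protocol.

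The cost is a change of SAP wording, one programming branch, and a data-entry clarification or query limited to events open at first dose. If there are no such events, the outputs do not change.

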4.0 STUDY DESIGN

4.1 Overall Design

This is a proof-of-concept, randomised, double-blind, placebo-controlled, multi-centre study designed to evaluate the safety/tolerability and efficacy of 4 sc injections of namilumab 150 mg given over 10 weeks as therapy in subjects with moderately-to-severely active axSpA, including those with a history of inadequate response to or intolerance to anti-tumour necrosis factor (TNF) therapy. The study will allow enrolment of up to 50% of subjects with primary non-response to prior anti-TNF treatment.

The study will consist of a maximum 4-week Screening period, followed by a 12-week doubleblind treatment evaluation period, followed by a 16-week safety follow-up period, for a maximum study duration of approximately 32 weeks or 224 days per subject. Eligible subjects will be randomised on Day 1 of Week 0 and receive study treatment administered sc on Day 1 of Week 0, Week 2 (loading dose), Week 6 and Week 10. Subjects will return on Week 12 for an End of Treatment (EoT) visit during which efficacy and safety assessments will be performed. Subjects will have a follow-up visit 16 weeks after the EoT visit.

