5.1 Inclusion Criteria

Subjects are eligible to be included in the study only if all of the following criteria apply:

- 1. Age ≥ 18 and ≤ 75 years of age.
- 2. Diagnosis of axSpA by an appropriately qualified physician and classified using ASAS criteria ≥3 months prior to Baseline; symptoms must have started before age 45.
- 3. Bath Ankylosing Spondylitis Disease Activity Index (BASDAI) score ≥4 and spinal pain score ≥40, at screening and Baseline.
- 4. MRI evidence of active axSpA ≤6 (ideally ≤3) months prior to randomisation using ASAS criteria.
- 5. A negative tuberculosis (TB) screening assessment.
- 6. A female subject of childbearing potential who is sexually active with a non-sterilised male partner agrees to routinely use adequate contraception from signing of the informed consent throughout the duration of the study until the end of the safety follow up (18 weeks after last dose) (see Appendix 7).
- 7. A male subject who is non-sterilised and sexually active with a female partner of childbearing potential agrees to use adequate contraception from signing of the informed consent throughout the duration of the study until the end of the safety follow up (18 weeks after last dose) (see Appendix 7).
- 8. Stable NSAID use for 28 days prior to study entry (see Appendix 5).
- Stable use of MTX (≤25 mg/week), sulfasalazine (≤3 g/day) or leflunomide (≤20 mg/day) for 28 days prior to study entry (see Appendix 5).
- 10. Stable oral corticosteroid dose ≤ 10 mg for 28 days prior to study entry (see Appendix 5).
- 11. Capable of giving signed informed consent as described in Appendix 2, which includes compliance with the requirements and restrictions listed in the informed consent form (ICF) and in this protocol.

In addition, the following inclusion criteria will apply for some subjects:

12. Inadequately responded to or experienced intolerance to previous treatment with an anti-TNF agent (limited to 50% of the total study population).

Note: Criteria for inadequate response to or experienced intolerance to previous treatment with an anti-TNF agent are defined as:

- Signs and symptoms of persistently active disease despite a history of at least one12week regimen of one of the following agents:
 - Infliximab: 5 mg/kg i.v.
 - Etanercept: 50 mg weekly
 - Adalimumab: 40 mg fortnightly
 - Golimumab: 50 mg monthly
 - Certolizumab pegol: 400 mg SC initially and at Weeks 2 and 4, followed by 200 mg every 2 weeks or 400 mg every 4 weeks

OR

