6.2.2 Handling

All study medications will be administered by the Investigator or designee.

The subject will visit the clinic for dosing of **binded** of blinded study medication by a single subcutaneous injection on Days 1, 15, 43 and 71.

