8.2.4.2 Chest X-ray

A baseline posterior-anterior (PA) chest x-ray taken no later than 3 months prior to the visit, with no clinically significant abnormalities consistent with PAP, should be available at screening. If no such x-ray is available, then subjects will be required to undergo this procedure at Baseline and assessment made before any study medication is administered to the subject at this clinic visit. Further x-rays will also be required during clinic visits at Weeks 12 and 28, respectively (as shown in SoA).

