15.1.5. Adverse Events of Special Interest

The following TEAEs of special interest (for which there is a specific tick box in the eCRF) will be summarized separately (but included in all other summaries):

- Pulmonary alveolar proteinosis (PAP)
- o Neutropaenia
- Myeloid suppression

 Document:
 x:\biostatistics\documentation\sap\pya18238_izana_izn-101_sap_v1_0_2019050.docx

 Author:
 Version Number:
 1.0

 Version Date:
 07May2019

Template No.: CS_TP_BS016 Revision 5

Effective Date: 01Apr2018

Copyright © 2009, 2010, 2012, 2016, 2018 IQVIA. All rights reserved. The contents of this document are confidential and proprietary to IQVIA Holdings Inc. and its subsidiaries. Unauthorized use, disclosure or reproduction is strictly prohibited.

Reference: CS_WI_BS00

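### The TEAE window closes 125 days after the last dose, one day short of the planned final safety visit at 126 days, so an adverse event dated to that visit can drop out of the TEAE and special-interest tables

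*SAP*

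**What the plan says.** The upper limit of the TEAE window is worded in three ways.

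- Protocol 9.4.2: "prior to 125 days after the last administration of study treatment".
- SAP 15.1: "prior to the last date of study medication + 125 days (inclusive".
- SAP 17, in the dating algorithm for a known start date: "If start date >= study med start date up to 125 after study med stop date, then TEAE".

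On timing, protocol 6.2.2 has study drug given "by a single subcutaneous injection on Days 1, 15, 43 and 71". Protocol 4.1 adds "Subjects will have a follow-up visit 16 weeks after the EoT visit". The Schedule of Activities (protocol 1.3) sets the last dose at Day 71 ±2, the End of Treatment (EoT) visit at Day 85 ±2 and the follow-up visit at Day 197 ±4. Inclusion criteria 6 and 7 give the length of safety follow-up in describing contraception "until the end of the safety follow up (18 weeks after last dose". Protocol 8.3.1 collects AEs up to the follow-up visit.

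That visit includes a chest x-ray (protocol 8.2.4.2: "Further x-rays will also be required during clinic visits at Weeks 12 and 28, respectively"), ECG, pulse oximetry, the MRC breathlessness scale and a physical examination. Under protocol 8.2.5, any incident that needs investigation for PAP is recorded as an AE of suspected PAP.

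On reporting, SAP 15.1.5 states "The following TEAEs of special interest (for which there is a specific tick box in the eCRF) will be summarized separately". Chest x-ray results are listed only (SAP 15.7.1.2).

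**The concern.** The visit that closes safety follow-up lies just outside the window that decides which events enter the safety tables. An event first noticed at that visit and given that date as onset is non-treatment-emergent if the subject came on the planned day, and treatment-emergent if the subject came a day or more early. Scheduling then decides the classification of clinically identical findings.

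PAP is the event for which this matters most. Protocol 8.2.5 sends a subject to a pulmonologist for a fall in oxygen saturation of more than 5% or an MRC rise of 2, and both are measured at Week 28. Protocol 8.3.6 says that characteristic x-ray changes come before severe symptoms, and only two post-dose x-rays are required. X-ray results have no table of their own, so the special-interest summary is where a reader would look for a PAP signal. One event among the 36 planned namilumab subjects is 1/36 = 2.8% in that table, or 0% if the window excludes it.

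**Working it through.** **1. The plan's own interval.** The protocol gives 18 weeks from last dose to end of safety follow-up: 18 × 7 = 126 days. Other entries agree:

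- Day 197 − Day 71 = 126
- (Week 28 − Week 10) × 7 = 126
- EoT Day 85 + 16 × 7 = Day 197

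**2. Last day of the window, with the last dose on Day 71.**

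- SAP, inclusive reading: 71 + 125 = Day 196
- Protocol, strict reading of prior to: Day 195

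An AE with known onset on Day 197 is outside by 1 or 2 days.

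**3. Range within the visit windows.** Let the last dose be on Day 71 + b (b from −2 to +2) and the follow-up visit on Day 197 + a (a from −4 to +4). The gap is 126 + a − b.

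- Shortest: 193 − 73 = 120 days
- Longest: 201 − 69 = 132 days

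**4. Number of combinations outside the window.** There are 9 × 5 = 45. On the inclusive reading the visit is outside when the gap exceeds 125 (a ≥ b). On the strict reading it is outside when the gap is 125 or more (a ≥ b − 1).

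| Last-dose shift b | Outside, inclusive | Outside, strict |
|---|---|---|
| −2 | 7 | 8 |
| −1 | 6 | 7 |
| 0 | 5 | 6 |
| +1 | 4 | 5 |
| +2 | 3 | 4 |
| Total of 45 | 25 (56%) | 30 (67%) |

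With the last dose exactly on Day 71, visits on Days 193 to 196 are inside and Days 197 to 201 outside on the inclusive reading.

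**5. Does another rule bring the event back?** SAP 15.1 assigns the worst case only when treatment emergence cannot be determined. A known visit date is determinable, so the rule does not apply.

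**6. Meaning of the stop date.** SAP 13.1 computes exposure to the last injection, and the steps above use that date. SAP 13 takes the date of last medication from the End of Treatment form. If the Week 12 visit date were programmed instead, the window would run to 85 + 125 = Day 210 and no in-window visit would be excluded.

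**7. Candidate limits.**

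- Last dose + 126 days covers 25 of 45 combinations.
- Last dose + 132 days covers 45 of 45, but only when the last dose was at Week 10.
- A subject who misses the Week 10 dose and keeps to the visit schedule has a gap of 197 − 43 = 154 days, which + 132 does not reach.

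**The case against.** The strongest defence is that 125 days is an exposure limit, deliberately separate from the visit calendar. Protocol 4.2.4 gives a half-life of 25 days, and 5 × 25 = 125. Protocol 8.4 uses at least 125 days as the time until drug is no longer detectable after an overdose. The link to the TEAE definition is an inference, but an exposure-based limit is a legitimate choice. It explains the number. It does not give a reason to exclude, by one day, the visit planned to close safety follow-up.

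Several points on that side stand and limit the size of the problem:

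- Nothing disappears from the report. AE listings include non-TEAEs (SAP 15.1), and details of SAEs and special-interest events are listed.
- ECG, vital signs, oximetry and the MRC scale have summaries that do not depend on TEAE status (SAP 15.4, 15.5, 15.7).
- No document sets an onset-dating rule for x-ray findings. If earlier symptoms are recorded as the onset, the event remains a TEAE.
- Scheduled Week 28 bloods are CRP and ESR only, so routine testing at that visit would not newly detect neutropaenia or myeloid suppression. Lung function tests are not scheduled then.

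A reader might infer that every finding at the final visit is excluded. The documents do not support this, since 20 of 45 window combinations fall inside the limit. A reader might also infer that the Week 28 x-ray is the one most likely to show PAP. Protocol 8.3.6 says only that x-ray changes come before severe symptoms. It does not rank Week 28 above Week 12, and it calls the risk after short-term dosing very low.

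**Conclusion.** The misalignment is real and small in days: one day on the SAP's inclusive wording, two on the protocol's strict wording. On the planned schedule, an AE with onset recorded at the final visit is always outside the window, and this needs no assumption beyond reading the stop date as the last injection. The 56% and 67% shares assume that every day in each window is equally likely. They describe visit timing, not the frequency of events.

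The consequence is confined to the AE summary tables: TEAE incidence, serious TEAEs and special-interest events. Within the special-interest group it concerns mainly suspected PAP. It is still worth correcting, because chance in scheduling should not decide how a safety event is classified. The text needs an edit in any case: SAP 15.1 says both prior to and inclusive for the same limit, and protocol 9.4.2 read strictly ends a day earlier.

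**What to change.** In SAP 15.1, the SAP 17 algorithm and protocol 9.4.2, use one wording for the upper limit: an AE counts if it starts on or after the first dose and no later than the later of (a) last dose + 125 days, inclusive, and (b) the date of the Week 28 follow-up visit. State that last dose means the last injection.

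Taking the later of the two dates keeps the 125-day limit for subjects who have no follow-up visit or attend early. It also covers subjects whose last dose was before Week 10, which a fixed + 132 days would miss.

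In SAP 15.1.5, summarise special-interest events with onset on or after the first dose regardless of the cut-off.

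The cost is a wording change and a small programming change before database lock. No efficacy result is affected. A few late events may be added to the TEAE tables.
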